7.2.1. Selection and Timing of Doses

This is a fixed-dose study. The actual time of all dose administrations will be recorded in the patient's electronic case report form (eCRF).

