## **5.5.10. Efficacy Analyses**

### **5.5.10.1. Primary Outcome and Methodology**

The primary efficacy objective is to assess whether at least 1 dose of LY2951742 (120 or 240 mg/month) is superior to placebo in the prevention of migraine headache in patients with episodic migraine.

The primary analysis will evaluate the efficacy of LY2951742 (120, or 240 mg/month) compared with placebo on the overall mean change from baseline in the number of monthly migraine headache days during the 6-month treatment phase.

The primary analyses will be performed using a REML-based MMRM technique. The analysis will include the fixed categorical effects of treatment, month, and treatment-by-month interaction, as well as the continuous fixed covariates of baseline number of migraine headache days and baseline-by-month interaction.

An unstructured covariance structure will be used to model the within-patient errors. The Kenward-Roger (Kenward and Roger 1997) approximation will be used to estimate denominator degrees of freedom. If the model does not converge, the Fisher scoring algorithm will be implemented by specifying the SCORING option (SCORING=5) in SAS. If the model still fails to converge, the model will be fit using covariance matrices of the following order specified by a decreasing number of covariance parameters until convergence is met:

- Heterogeneous Toeplitz = toeph
- Heterogeneous First-order autoregressive = arh(1)
- Toeplitz = toep
- First-order autoregressive = ar(1)

Hence we fit the model by the following order:

- [1] unstructured covariance with the default fitting,
- [2] unstructured covariate with the Fisher scoring,
- [3] toeph covariance with the default fitting,
- [4] toeph covariance with the Fisher scoring
- [5] arh(1) covariance with the default fitting,
- [6] arh(1) covariance with the Fisher scoring
- [7] toep covariance with the default fitting,
- [8] toep covariance with the Fisher scoring
- [9] ar(1) covariance with the default fitting,
- [10] ar(1) covariance with the Fisher scoring

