### **5.5.13. Subgroup Analyses**

Subgroup analyses will be performed for primary efficacy measure (change from baseline in the number of monthly migraine headache days) only for the ITT patients in the 6-month treatment phase unless otherwise specified. [Table CGAN. 5.8](#) provides definitions for each subgroup variable. Subgroup variables are usually selected if they are potentially prognostic or predictive. A subgroup variable is prognostic if values of the subgroup variable predict the change in efficacy measures regardless of the treatment group assignment. A subgroup variable is predictive if values of the subgroup variable predict heterogeneous treatment effect. Current understanding is that demographic subgroup variable sex is not prognostic nor predictive. But they are standard subgroup variables needed for regulatory submission. The rest of subgroup variables determined before Visit 3 injection are expected to be prognostic. The purpose of the analyses for these subgroup variables is to assess the consistency of treatment effects across the different values of each subgroup variable.

Table CGAN. 5.8 Definition of Subgroup Variables

Subgroup Variable	Categories
Sex	Male, female
Baseline category of MHD (Visit 2 to Visit 3)	2 levels of baseline migraine frequency : 
 
• <8 migraine headache days per 30-day period
 
• ≥8 migraine headache days per 30-day period
 

Treatment resistant status (Visit 1)	Treatment resistant status about whether a patient has failed two or more prophylactic treatments (migraine preventive therapy): Yes vs No
Having aura or not (during baseline Visit 2 to Visit 3 period)	Yes vs No (a patient with aura is defined as a patient who answers “yes” to at least one day of ePRO Question 12 “Yesterday, did you experience aura?” during prospective baseline period)
Baseline anti-drug antibody status (Visit 3)	Any confirmed positive anti-drug antibody at baseline (Yes vs No)
Neutralizing anti-drug antibody status (SP II and SP III)	Any positive neutralizing anti-drug antibody time point (Yes vs No) – note that neutralizing anti-drug antibody assays are performed only on confirmed-positive anti-drug antibodies
Treatment-emergent anti-drug antibody status (SP III)	Any treatment-emergent anti-drug antibody (Yes vs No)
Baseline body weight (last observation before Visit 3 injection)	2 levels (weight ≤ median, median < weight).

Abbreviations: MHD = migraine headache days.

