For subgroup analyses, the subgroup-by-treatment interaction will be tested at a 2-sided 0.1 significance level. Treatment group differences will be evaluated within each category of the subgroup variable.

The subgroup analyses for primary will be conducted using MMRM. The same MMRM model as described in Section 5.5.10.1 will be used with terms of subgroup, subgroup-by-treatment, subgroup-by-month, and subgroup-by-treatment-by-month interactions added as additional covariates. In this analysis, the p-value for the subgroup-by-treatment, subgroup-by-month, and subgroup-by-treatment-by-month interactions will be reported.

For the analysis within a subgroup using MMRM, the LSMean change estimates as well as the treatment comparisons within each subgroup will be conducted with the data within that specific subgroup. The MMRM model will be the same as described in Section 5.5.10.1. For each category of the subgroup variable, comparisons between each treatment group with placebo will be assessed during the 6-month post-baseline period.

50% response rate (one of the key secondary analysis) will be performed by the treatment resistant status subgroup, (simply using 2 different subgroups with the same covariates)

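### Consistency of effect across body weight and baseline migraine headache days is tested only on two-level cuts; adding continuous interaction terms would be a cheap gain in sensitivity

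*SAP*

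**What the plan says.** Table CGAN. 5.8 in SAP section 5.5.13 defines the subgroup variables. Baseline body weight, which the SAP revision history lists as a Version 2 addition, is split at the sample median: "2 levels (weight ≤ median, median < weight"). Baseline MHD has "2 levels of baseline migraine frequency", below 8 and 8 or more per 30 days.

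On testing, section 5.5.13 states that "the subgroup-by-treatment interaction will be tested at a 2-sided 0.1 significance level". The model is the primary MMRM with "subgroup, subgroup-by-treatment, subgroup-by-month, and subgroup-by-treatment-by-month interactions added as additional covariates". Treatment differences are also estimated within each category. For the variables known before the first injection, other than sex, the aim is given as follows: "The purpose of the analyses for these subgroup variables is to assess the consistency of treatment effects across the different values".

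The primary MMRM (SAP 5.5.10.1) already carries the "continuous fixed covariates of baseline number of migraine headache days and baseline-by-month interaction". Baseline MHD is therefore continuous as a main effect and by month, but has no continuous interaction with treatment. Protocol 7.2.1 adds: "This is a fixed-dose study".

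The cut at 8 MHD is also the randomization stratum (Protocol 7.2; SAP 5.3).

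**The concern.** Weight is continuous and baseline MHD is close to it: a 4-to-14 count normalized to 30 days. With a fixed dose, the natural question is a graded one: does the difference from placebo shrink as weight rises, or change with headache frequency? A two-level cut treats patients just either side of the boundary as different, and patients far apart on the same side as alike. A gradual trend is then harder to detect, and the output cannot give the change in effect per kilogram or per baseline day.

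The stake is modest but real. In a bridging study, a non-significant interaction may be read as evidence of consistency. If the test is less sensitive than the data allow, that reading is weaker than it looks. A slope with its confidence interval would show which trends have been excluded and which have not.

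**Working it through.** **1. The plan's own figure.** The documents give no power for the interaction tests. The nearest figure is the approximately 88% power for at least one dose in the primary comparison (Protocol 10.1; SAP 5.2). Inputs are 225/113/113 patients, effect size 0.36, 15% discontinuation and a two-sided Dunnett test at 0.05. Completers are 0.85 × 225 ≈ 191 and 0.85 × 113 ≈ 96 per dose, 383 in all. Monte Carlo with critical value 2.236 gives 89.4%, so the figure reproduces. The same 191/96/96 is used below, with one six-month average per patient as an approximation to the MMRM.

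**2. Information kept by a cut.** If the treatment difference is linear in X and D is the two-level version, with q the share in the upper group, the fraction kept is

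corr(X, D)² = Cov(X, D)² / [Var(X) × q(1 − q)].

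- Normal X split at the median: 0.3989² / (1 × 0.25) = 2/π = 0.637.
- Whole-number MHD, uniform on 4 to 14, cut at 8: mean 9, variance 10, q = 7/11, covariance 1.273. This gives 1.273² / (10 × 0.2314) = 0.70.

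The documents give neither distribution, so the range over assumed shapes is:

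| Variable and assumed shape | Kept | Lost |
|---|---|---|
| Weight, normal | 64% | 36% |
| Weight, lognormal, log-SD 0.10 to 0.20 | 63% to 62% | 37% to 38% |
| Weight, lognormal, log-SD 0.30 (strong skew) | 59% | 41% |
| MHD, continuous, flat to exponentially declining on 4–14 | 72% to 74% | 26% to 28% |
| MHD, whole-number uniform | 70% | 30% |
| MHD, truncated Poisson, mean 7 to 9 | 68% to 61% | 32% to 39% |
| MHD, truncated normal, 30% to 70% of patients below 8 | 71% to 59% | 29% to 41% |

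The upper limit of 70% below 8 matches the enrollment cap: 315/451 = 0.70. At 64% kept, 383 completers carry the information of 0.637 × 383 ≈ 244 on a linear weight trend.

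**3. Effect on power.** With two doses the interaction test has 2 df; at 0.10 the chi-square critical value is 4.605. Power of 80% needs noncentrality λ = 7.71. Multiplying λ by the fraction kept gives:

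- 0.637 × 7.71 = 4.91: power 62% (weight, normal)
- 0.74 × 7.71 = 5.71: power 68% (MHD, best case)
- 0.59 × 7.71 = 4.55: power 59% (MHD, worst case)

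**4. Dependence on the slope.** Let the difference from placebo change by b outcome SDs per SD of weight, equally in both doses. Then λ = b² × 191 × 192 / 383 = 95.75 b² on the continuous scale, and 0.637 times that after the split.

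| b (assumed) | Power, continuous | Power, median split |
|---|---|---|
| 0.10 | 21% | 17% |
| 0.15 | 35% | 26% |
| 0.20 | 53% | 38% |
| 0.30 | 84% | 67% |

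Simulated F tests (4,000 trials each) agree: 83% against 65% at b = 0.30, 52% against 39% at b = 0.20, and a type I error of about 10% for both at b = 0.

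**5. How steep is b = 0.30?** Against the planned effect size of 0.36, the effect would be 0.36 + 0.30 = 0.66 at one SD below mean weight, 0.36 − 0.30 = 0.06 at one SD above, and zero at 0.36/0.30 = 1.2 SD above. That is a strong trend.

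**The case against.** Nothing in the plan is breached. The subgroup analyses are supportive, the 0.10 level is already lenient, and the SAP plans no claim about effect per kilogram. The cut at 8 MHD is not arbitrary: it is the randomization stratum, the basis of the enrollment cap, the stratum of the log-rank tests and a covariate in other models. Testing the interaction on a stratification factor is normal practice. For mild trends both tests are weak, so the change would seldom alter a conclusion. Protocol Table CGAN.4.1 also lists an exploratory exposure-response analysis, and pharmacokinetics go to a separate plan that is not in these documents.

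Most of this stands. It justifies keeping the two-level tables and limits the weight of the point. It does not remove it: the exposure-response analysis relates serum concentration to outcome and does not replace a randomized treatment-by-covariate comparison. A stratum is a reason to display the cut, not a reason to test only on it.

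Some stronger readings are tempting, and the documents do not support them. One is that the cut discards a known share of the information; that share depends on distributions the documents do not give and on a linear trend. Another is that baseline MHD is dropped as a continuous variable; it stays in the model, and only its interaction with treatment is cut. A third is that a sample-median split prevents comparison with weight groups in the global studies. Those studies' subgroup definitions are not in the documents and the bridging criteria are redacted. All that can be said is that a sample median is not fixed in kilograms in advance.

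**Conclusion.** The point holds as an inexpensive improvement to a supportive analysis. Section 5.5.13 tests consistency for two graded variables only on cut versions, and the readable text plans no continuous interaction.

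Under a roughly linear trend and the assumed distributions, the loss is about 36% to 38% for normal or mildly skewed weight and about 26% to 41% for baseline MHD. A test with 80% power on the continuous scale falls to about 62% and 59% to 68% respectively. The gain from the change is clear for steep slopes and small for shallow ones. It vanishes if the effect steps at the cut. A reader should not infer any weakness in the primary result: the primary MMRM, the step-down Dunnett procedure and the sample size are untouched.

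**What to change.** In SAP section 5.5.13, add two prespecified interaction analyses on the primary MMRM:

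- **Weight:** continuous baseline weight with its treatment, month and treatment-by-month interactions, mirroring the terms planned for the two-level version.
- **Baseline MHD:** treatment-by-baseline-MHD and treatment-by-baseline-MHD-by-month, added to the continuous baseline terms already in the model.

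For each, report the slope of each dose-placebo difference with its 95% CI, and the estimated difference at the 10th, 50th and 90th percentiles. Include a simple linearity check, such as a quadratic or spline term. Keep the two-level tables of Table CGAN. 5.8, including the display by the cut at 8.

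The cost is a few lines of SAP text and a few extra model terms; no new data are needed. The downside is that a linear trend is assumed, which the linearity check and the retained tables guard against, and there is a little more to analyze and report. To count as prespecified, the terms must be fixed before unblinding; after that they should be labelled supplementary.

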## 5.6. Interim Analyses

An interim analysis is planned when all randomized patients have had the chance to complete or discontinue 6 months of treatment (SP III) and, thus, will be the final analysis of the primary efficacy endpoint. The interim analysis will be conducted by internal unblinded study team members who do not have direct interaction with sites (Section 5.7). The primal intention of the interim analysis will be for Japan regulatory submission.

## 5.7. Unblinding Plan

During the study, some members are unblinded (Table CGAN. 5.9). These members will not be allowed to join meetings which may affect the other members' blind condition, such as trail level safety review (TLSR) and data review meetings.

**Table CGAN. 5.9 Unblinded members through CGAN Study**

Role	Reason	Data source for unblinding
Product Delivery personnel	To provide and manage Clinical trial materials	e-CTS
Clinical Laboratory Operations	To manage and track sample shipping	CLRM
Unblind Case Manager	To report SAE with unblinded information to EU authority	e-CTS
Data Movement	To transfer unblinded data at the timing of interim DBL (and final DBL)	source data of CLUWE

Abbreviations: CLRM = Clinical Laboratory Results Modernization; DBL = database lock; e-CTS = Enhanced Clinical Trials System; EU = European Union; GPS = Global Patient Safety; IWRS = interactive web-response system; PK/PD = pharmacokinetics/ pharmacodynamics; SAE = Serious Adverse Event.

The interim analysis will be conducted by selected unblinded study team members who do not have direct interaction with sites (Table CGAN. 5.10). These members will become unblinded after the interim database lock. All study personnel with direct interaction with sites are kept blinded to the interim analysis results.

**Table CGAN. 5.10 Unblinded members after the interim database lock**

Role	Reason	Data source for unblinding
Project Statistician	CSR/PMDA consultation preparation	CLUWE/TFL
Statistical Analyst	CSR/PMDA consultation preparation	CLUWE/TFL
Statistical Analysis programmers	CSR/PMDA consultation preparation	CLUWE/TFL
Medicals (Clinical Research Scientist, Clinical Research Physician)	CSR/PMDA consultation preparation	TFL
PK/PD	CSR/PMDA consultation preparation	CLUWE/TFL
Medical Writer	CSR/PMDA consultation preparation	TFL
CPM	CSR/PMDA consultation preparation	TFL
CTPM	CSR/PMDA consultation preparation	TFL
PPM	CSR/PMDA consultation preparation	TFL
Regulatory	CSR/PMDA consultation preparation	TFL
Data Management	CSR/PMDA consultation preparation	CLUWE/TFL

Abbreviations: CPM = Clinical Project Manager; CLUWE = Clinical Users Working Environment; CSR = Clinical Study Report; CTPM = Clinical Trial Project Management; PK/PD = pharmacokinetics/ pharmacodynamics; PMDA = Pharmaceuticals and Medical Devices Agency; PPM = Product Project Manager; TFL = tables, figures, listings;

## 5.8. Reports to be Generated at Interim and Final Database Lock

### 5.8.1. Report to be Generated at Interim Analysis

At the time of interim analysis, all randomized patients will have had the chance to complete 6 months of treatment. The following analyses will be conducted for pre-specified population (e.g. ITT, safety population) in the SAP who have had a chance to complete 6 months of treatment:

- Patient disposition as specified in Section 5.5.2, but for Study Period III only.
- Protocol deviations as specified in Section 5.5.3, but for Study Period III only.
- Patient Characteristics as specified in Section 5.5.4.
- Exposure to Investigational Product as specified in Section 5.5.5.

- Treatment Compliance as specified in Section 5.5.6.
- ePRO Diary Compliance as specified in Section 5.5.7, but for Study Period III only.
- Previous Migraine Prevention Therapy and Previous Migraine Acute Treatment as specified in Section 5.5.8.
- Concomitant Therapy, Migraine Prevention Therapy and Migraine Acute Treatment as specified in Section 5.5.9, but for Study Period III only.
- All efficacy, quality-of-life and safety analyses as specified in Section 5.5.10, Section 5.5.11 and Section 5.5.12, but for Study Period III only except immunogenicity related analysis. Immunogenicity related analysis will not be conducted at the interim DBL because some data during SP III will not be included in the interim DBL due to time lag.
- Subgroup analyses as specified in Section 5.5.13.
- Bridging Criteria as specified in Section 5.10.

Some TFLs at interim analysis may contain both SP III and SP IV data (e.g. HCRU summary). Those TFLs will be updated at the final DBL.

Analysis for “SP III and SP IV combined” and “SP IV only” (e.g. time from the end of SP III to start of migraine prevention treatment in SP IV), and ADA related analysis will be based on the final DBL.

The TFLs for SP III only (i.e. no use of SP IV data) based on the interim DBL will be used in the final study Clinical Study Report (CSR) except for some TFLs needed to be updated. Hence analysis conducted at the interim DBL which do not include SP IV data will not be refreshed at the final DBL unless otherwise specified. Those TFLs will be specified and explained in CSR, if they exist.

### **5.8.2. Report to be Generated at Final Database Lock**

For the final database lock, all TFLs will be created except for those which will be created and finalized at the interim analysis. At the timing of final database lock all randomized patients will have had a chance to complete or discontinue 6 months of treatment period (SP III) and 4 months of the post-treatment period (SP IV.)

Analyses at final lock combined with the analysis from interim analysis will be used in the final CSR.

## **5.9. Clinical Trial Registry Analyses**

Additional analyses will be performed for the purpose of fulfilling the Clinical Trial Registry (CTR) requirements. These analyses will be the responsibility of the Sponsor.

Analyses provided for the CTR requirements include the following:

A summary of AEs will be provided as a dataset which will be converted to an XML file. Both SAEs and ‘Other’ AEs are summarized: by treatment group, by MedDRA PT (SP III and SP IV separately).

- An AE is considered ‘Serious’ whether or not it is a TEAE.
- An AE is considered in the ‘Other’ category if it is both a TEAE and is not serious. For each SAE and ‘Other’ AE, for each term and treatment group, the following are provided:
  - the number of participants at risk of an event
  - the number of participants who experienced each event term
  - the number of events experienced.
- Consistent with [www.ClinicalTrials.gov](http://www.ClinicalTrials.gov) requirements, ‘Other’ AEs that occur in fewer than 5% of patients in every treatment group may not be included if a 5% threshold is chosen.
- AE reporting is consistent with other document disclosures for example, the CSR, manuscripts, and so forth.

### 5.10. Bridging Criteria

[Redacted text block containing multiple paragraphs of blacked-out content with 'CCI' labels in red.]

[REDACTED] CCI [REDACTED]  
[REDACTED]  
[REDACTED]  
[REDACTED]

